1. PURPOSE AND BACKGROUND

1.1. Purpose

Primary Objective:

To test whether fluoxetine, a selective serotonin reuptake inhibitor (SSRI) previously demonstrated to enhance post-stroke motor recovery, also enhances post-stroke visual recovery in ischemic stroke survivors.

Secondary Objectives:

- (1) To understand whether a putative fluoxetine effect is mediated through a drug-specific mechanism (*e.g.* a fluoxetine-dependent increase in neural plasticity), or rather through indirect mechanisms, such as general improvements in mood and motivation to participate in rehabilitation, resulting from the antidepressant actions of the drug.
- (2) To track the natural history of post-stroke visual recovery using a combination of clinical and radiographic approaches, including standard neuro-ophthalmologic evaluations, measures of retinal nerve fiber layer (RNFL) thickness, visual and general disability measures, neuropsychological testing, and functional magnetic resonance imaging (fMRI).
- (3) To estimate the feasibility of larger future clinical trials studying the effects of various pharmacological or behavioral interventions on the rate and degree of post-stroke visual recovery.
- (4) To use the information gathered from the above objectives to study the physiologic mechanisms of spontaneous post-stroke visual recovery, with the goal of identifying better targets for therapeutic interventions.

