The visual cortex offers the ideal model system for testing hypotheses about mechanisms of neural plasticity that may be engaged by SSRIs in the post-stroke recovery period. First, in contrast to motor recovery, motivation probably plays a less prominent role in post-stroke visual recovery, as most spontaneous recovery probably occurs early (10) and rehabilitative interventions typically focus on teaching patients compensatory techniques. Second, it is known that fluoxetine can reopen critical periods of neural plasticity in the adult rodent visual system (11). Third, structure-function relationships in the visual system are well understood. The early visual cortex in particular has a highly regular retinotopic organization. Post-stroke changes in this retinotopic map can be characterized and followed by fMRI. Furthermore, cerebral infarction can lead to retinal ganglion cell degeneration through a retrograde trans-neuronal mechanism (12), providing another window through which post-stroke changes in the visual pathway can be monitored and quantified using non-invasive techniques such as optical coherence tomography (OCT). Our research team has demonstrated expertise in characterizing early visual system organization in clinical populations (13). Thus, we are well positioned to assess whether

any observed effects of fluoxetine on post-stroke recovery are due to quantifiable changes in neuronal survival and neural plasticity.

Potential future directions

Fulfillment of this research program has the potential to alter our clinical approach to ischemic strokes affecting the visual system. In addition, answering these questions in the visual system may have more general implications. An understanding of the dynamics and limits of neural plasticity in the post-stroke visual cortex will likely enable us to formulate and test specific hypotheses about how therapeutic interventions like fluoxetine may promote recovery from ischemic strokes affecting other higher-order cognitive functions, including language, praxis, memory, attention, and executive function.

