9. Functional magnetic resonance imaging (fMRI): Visual processing will be assessed using fMRI. Dependent measures will consist of high-resolution measurements of cortical thickness and representation, functional activity during visual tasks as measured by blood oxygen level-dependent (BOLD) responses, and measurements of the structural integrity of nerve fibers in the brain using diffusion tensor imaging. Subjects will be asked to view and respond to a visual stimulus according to the specific task description. For example, they may be asked to name common objects depicted in a picture, or estimate the number of dots in a display. Typically subjects will be asked to perform a task in the MRI machine for 45 minutes, although sessions may go up to 70 minutes depending on the comfort and compliance of the study participant. Tasks will be broken up into shorter runs of 5 to 10 minutes in order to

allow participants to rest during the testing session. Scanning will occur on MRI machines at Strong Memorial Hospital, the University of Rochester Stroke and Cerebrovascular Disorders Clinic, or the RCBI. Study integrity will not be compromised by scanning a given patient on different scanners at different times. We will compute contrasts only between experimental conditions tested on the same machine during the same scan, so the key effects we measure will be orthogonal to any scanner variation. Finally, fMRI data will be retained in an anonymized form for future use by other researchers as part of this study.

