Subjects will be screened for magnetic material before each study using an MRI safety screening form (Appendices D1, D2, and D3). Those with pacemakers, implantable cardiac defibrillators, aneurysm clips, penile implants, metallic prostheses including heart valves and cochlear implants, and bullet or shrapnel fragments are at risk of injury in an MR environment. Welders and metal workers are also at risk because of possible metal fragments in their eyes. Those at risk will be excluded from the study.

Scanning by MRI produces a loud tone that can cause injury to the inner ear if appropriate protection is not used. Earplugs or close-fitting silicone-padded headphones will be provided to each subject to prevent ear injury.

The long-term health risks of MRI are unknown. This study will use a magnetic field strength of 3.0 Tesla, which is commonly used in clinical practice and research. This field strength has been used in the clinical setting for nearly a decade, and so far no detrimental long-term effects have been identified.

Phlebotomy: Risks associated with phlebotomy include pain or stinging when the needle is inserted and throbbing and/or bruising at the puncture site after the blood is drawn. To reduce the risk of bruising, subjects will be instructed to hold pressure on the puncture site for several minutes after the needle is withdrawn. Rarely the vein may become inflamed after the blood sample is obtained. This is treated with a warm compress applied several times a day. Finally, there is a small risk of infection at the puncture site. This risk will be minimized by the use of proper sterile technique.

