13.2. Planned Statistical Analysis

The primary endpoint will be an improvement in peripheral vision of at least 15 degrees in the affected visual field as measured by automated Humphrey perimetry at 6 months. The primary outcome will be compared between the treatment groups using an upper-tailed two-sample *t* test with $\alpha = 0.05$. Secondary outcome measures will include degree of cortical reorganization as assessed by fMRI, RNFL thickness as assessed by OCT, the functional vision score as assessed by the Guide for the Evaluation of Visual Impairment,

performance on neuropsychological testing, and scores on the mRS, PHQ-9, and VFQ-25.

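### The assurance that changing MRI scanners is harmless is supported only for task contrasts within one scan; it does not cover cortical thickness, diffusion measures, or gain differences in between-visit change

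*Combined protocol and SAP*

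**What the plan says.** Section 5.2, item 9 allows scanning at three locations (the hospital, the stroke clinic and the RCBI) and states: "Study integrity will not be compromised by scanning a given patient on different scanners at different times". The reason follows: "We will compute contrasts only between experimental conditions tested on the same machine during the same scan", from which the item concludes that the key effects are orthogonal to scanner variation.

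The same item defines the outcomes: "Dependent measures will consist of high-resolution measurements of cortical thickness and representation", then BOLD activity during visual tasks, then "measurements of the structural integrity of nerve fibers in the brain using diffusion tensor imaging".

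Follow-up over time is intended. Section 1.1, secondary objective 2, is to "track the natural history of post-stroke visual recovery using a combination of clinical and radiographic approaches", with fMRI among them. Section 1.2 says "Post-stroke changes in this retinotopic map can be characterized and followed by fMRI". The schedule Table places fMRI at baseline, 30 days, 90 days and 6 months, and section 13.2 says "Secondary outcome measures will include degree of cortical reorganization as assessed by fMRI".

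Two statements limit the problem. Section 10.1 gives the field strength as 3.0 Tesla. It also says "Subjects will be screened for magnetic material before each study using an MRI safety screening form", and Appendices D1 to D3 are separate forms by site, so the scan site should be traceable. No section says which scanner is used at which visit, and no analysis uses the scanner.

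**The concern.** The assurance is about the whole study, but its reason is about one kind of measurement. Cortical thickness and diffusion measures have no task conditions to subtract. Nothing in the plan removes a scanner difference from their change between visits, so such a difference could be read as recovery or degeneration. Even for task contrasts, the stated rule works inside a scan, whereas objective 2 needs comparisons between scans.

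The practical risk is that the sentence is taken as permission to schedule scans wherever convenient and not to carry the scanner into the dataset. If scanner and visit then coincide, no later analysis can separate them.

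**Working it through.** The plan states no figure on this point, so there is none to reproduce. The check is one of logic, followed by an illustration with assumed values.

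**Step 1. What same-scan subtraction removes.** Model a reading as offset + gain × signal. Take signal 1 in the active condition and 0 in the control condition, no true change between visits, and a first scanner with offset 0 and gain 1.

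- Within-scan contrast = (offset + gain × 1) − (offset + gain × 0) = gain.
- Non-contrast reading = offset + gain × 1.

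| Second scanner | Apparent change, task contrast | Apparent change, non-contrast measure |
|---|---|---|
| Offset 0.5, gain 1 | 1 − 1 = 0 | 1.5 − 1 = 0.5 |
| Offset 0, gain 1.05 | 0.05 | 0.05 |
| Offset 0, gain 1.10 | 0.10 | 0.10 |
| Offset 0, gain 1.20 | 0.20 | 0.20 |

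So the protocol's argument is right for an additive offset in a task contrast. It fails for a gain difference in between-visit change, and it does not apply to thickness or diffusion.

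**Step 2. Illustration for a non-contrast measure.** From section 13.1: 30 patients, 15 per arm. Assumed, because the documents give none of these: switching share q, offset b in SDs of change, share d of switches going in one direction, and a two-sided 5% one-sample t test of change when there is none.

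Bias in mean change = q × b × (2d − 1).

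| q | b | d = 1 | d = 0.75 | d = 0.5 |
|---|---|---|---|---|
| 25% | 0.2 | 6% | 5% | 5% |
| 50% | 0.5 | 25% | 10% | 5% |
| 100% | 0.5 | 75% | 23% | 5% |

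The entries are false-positive rates from simulation. With everyone switching one way, the noncentral t distribution (29 df) gives the rate directly: b = 0.5 has noncentrality 0.5 × √30 = 2.74 and rate 75%; b = 0.2 has 0.2 × √30 = 1.10 and rate 19%.

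**Step 3. Comparison between arms.** If switching is unrelated to arm, the bias is the same in both arms and cancels in expectation. The added variance is b²q − [qb(2d − 1)]². At q = 0.5 and b = 0.5:

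- one-way switching: 0.125 − 0.0625 = 0.0625, so 30 patients act like 30/1.0625 = 28.2;
- evenly split: 0.125 − 0 = 0.125, so they act like 30/1.125 = 26.7.

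Simulated false positives for the arm comparison stay at 5%. If everyone switches one way (q = 1, d = 1), the added variance is 0.

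**Step 4. What a scanner term would cost.** Assume 30 patients, four visits, all baselines on one scanner, change SD 1 (residual variance 0.5 per visit), and a model with patient, visit and scanner effects.

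- If switchers stay on the second scanner for every follow-up, SE² of mean change = (1/30)[1 + (2/3) q/(1 − q)]. This gives √(1.667/30) = 0.24 at 50%, √(3.667/30) = 0.35 at 80%, √(7/30) = 0.48 at 90%, and no estimate at 100%.
- If each follow-up scan is switched independently, simulation gives 0.20, 0.26 and 0.33 at 50%, 80% and 90%.

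Without a scanner term or scanner effect, SE = 1/√30 = 0.18. Expected same-scanner pairs are 30 × 0.2 = 6 at 80% and 30 × 0.1 = 3 at 90%.

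**The case against.** The case for leaving the text alone is substantial.

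- **The item may mean task contrasts only.** It speaks of key effects, and for an additive offset its argument is correct. This stands, but the sentence about study integrity is then wider than its support and should be narrowed.
- **The longitudinal text names fMRI, not thickness or diffusion.** Objective 2 and section 13.2 do not mention those two measures; only section 5.2, item 9 does. The false-positive rates above model an offset, so they cannot be carried over to the task-based reorganization outcome, where the remaining risk is a gain difference. This stands.
- **No test of mean change is planned.** Section 13.2 gives no analysis method for any secondary outcome, so the rates belong to an assumed test. They are also sensitive to the assumptions: with three scanners (offsets 0, 0.5 and −0.3 SD) used at random in follow-up, the bias is about 0.07 SD and the false-positive rate 6%. This stands.
- **Existing limits.** A common field strength removes one source of difference, and the screening forms reveal the site. Both help, but neither puts the scanner into an analysis.

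A reader might infer that scanner and visit are in fact confounded. Baseline takes place during the hospital stay (sections 2.1 and 5), and follow-up neuropsychological sessions are at the RCBI (section 5.2, item 8). If fMRI follows that route, switching would be frequent and mostly one way. That is plausible, but no section assigns scanners to visits, so the documents do not establish it.

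**Conclusion.** The point holds in a limited form. The assurance is justified for task contrasts within one scan. It is not justified for cortical thickness or diffusion, nor for between-visit change in task contrasts when scanners differ in gain. That much follows from section 5.2, item 9 alone.

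The consequence is confined to within-patient change in secondary imaging measures. Its size cannot be determined from the documents. The 5% to 75% range is an illustration that depends on an assumed switching rate, direction, offset and test, and applies to non-contrast measures only.

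Three stronger readings are not supported. The trial's main result is not threatened: the primary endpoint is Humphrey perimetry. The comparison of arms is not biased in expectation by switching unrelated to arm. And it is not shown that every between-visit imaging change is distorted, since an additive offset does cancel from task contrasts. I would class this as a minor correction, worth making because prevention is cheap before scanning and may be impossible afterwards.

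**What to change.** **Section 5.2, item 9.** Replace the general assurance with text to this effect: task contrasts are computed within one scan; change in cortical thickness and diffusion measures, and between-visit change in other imaging measures, can be affected by a change of scanner; each subject's serial scans will be done on the same scanner where possible; the scanner used at each visit will be entered in the study dataset.

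**Section 13.2.** Add that between-visit imaging change will be reported with the numbers of same-scanner and different-scanner pairs. Where scanner and visit overlap enough to fit it, give an estimate adjusted for scanner identity, with same-scanner pairs as a sensitivity analysis. Scanner identity is preferable to a yes/no switch indicator, so that opposite switches receive opposite corrections. Where scanner and visit largely coincide, report that change from baseline cannot be separated from scanner.

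The adjusted model should not be fixed as the main analysis, because its value depends on the switching pattern that occurs. It removes offsets, not gain differences, and a handful of same-scanner pairs cannot be said to cover the latter.

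**Cost.** A scheduling preference that may not be achievable for inpatient baselines, one data field, and some added reporting. Where the scanner term is used, precision falls: the SE of mean change is about 0.20 to 0.24 SD at 50% switching, 0.26 to 0.35 at 80% and 0.33 to 0.48 at 90%, against 0.18 unadjusted, and there is no estimate at 100%.

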5.3. Safety Assessments

Subjects will be instructed to exercise caution when drinking alcohol or taking any previously prescribed sedating medications, such as diphenhydramine or cyclobenzaprine, while on the study drug. Additionally, they will be advised to contact their primary care physicians or the study team before starting any new prescription or over-the-counter medications, or any new herbal or nutritional supplements. Primary care physicians will be provided with a list of medications and supplements to avoid while their patients are on the study drug.

Laboratory studies: A CBC and CMP will be repeated 30 days after the initiation of the study drug to monitor for any hematologic or metabolic abnormalities. This will require a total of 9 mL of blood to be collected from each subject.

ECG: An ECG will be obtained at baseline and at 30 days to measure each subject's QT interval and monitor for QTc prolongation or other arrhythmias.

Adverse event survey: A questionnaire to screen for adverse events will be administered by study personnel at 7 days by phone interview (Appendix H). This 7-day evaluation will be done in person if the patient has not been discharged from the hospital yet. The same questionnaire will be administered when the subjects return to the University of Rochester Stroke and Cerebrovascular Disorders Clinic for their follow-up visits at 30 and 90 days. Finally, the same questionnaire will be administered at 6 months by phone interview.

5.4. Data and Specimen Banking for Future Research Use

The data generated in this study may be used in future research in an anonymized form that cannot be connected to any individual subject. Data may also be shared with other researchers, but only after all identifying information has been removed to ensure subject confidentiality. Information recorded on paper will be stored inside a locked cabinet in a locked office as previously described. All digital data will be password-protected and stored on a firewalled server.

5.5. Costs to the Subject

There will be no planned costs to the subject for participation in this study. All study drugs will be provided free of charge. Neurological and neuro-ophthalmological evaluations performed as part of standard care at baseline, 30 days, 90 days, and 6 months will be billed to the patient's insurance. Additional study-specific evaluations that fall outside standard care (see Table) will be covered by the research program. Should a subject suffer any adverse outcomes as a result of participation in the study, the subject and/or the subject's insurance may need to cover the costs of any additional medical treatment

required.

5.6. Payment for Participation

Upon completing the study, each subject will receive a \$50 Visa® prepaid debit card as a token of appreciation for his or her participation. In addition, parking expenses will be covered for all follow-up visits.

5.7. Return of Individual Research Results

Individual research results will not be routinely made available to study subjects. However, they will have access to many of their test results upon request or through the online patient medical record access system, MyChart. With the exception of the serial fMRI studies, baseline and 60-day OCT studies, the PHQ-9, VFQ-25, and adverse event questionnaires, and the ECG, CBC, CMP, and Humphrey visual field testing performed at 30 days, all proposed evaluations are part of the routine care and work-up of stroke patients with visual field deficits. Results of these evaluations will be included in the medical record. Any incidental findings of potential clinical significance, discovered in the course of a study-specific evaluation that falls outside standard care, will be immediately disclosed to the patient and his or her primary care physician. Follow-up studies or consultations will also be recommended to the primary care physician as appropriate.

6. CONCOMITANT AND DISALLOWED MEDICATIONS

Subjects will be randomized to 20 mg of fluoxetine vs. placebo as previously described. During the course of the study, they will not be allowed to take higher doses of fluoxetine or any other SSRIs. Additionally, in order to reduce the risk of any adverse events due to drug-drug interactions, they will not be allowed to take medications contraindicated in combination with SSRIs, including other SSRIs, non-selective serotonin reuptake inhibitors, monoamine oxidase inhibitors, tricyclic antidepressants, and QTc-prolonging agents.

7. SUBJECT WITHDRAWALS

Subjects will be advised on the written informed consent form (Appendix A) that they have the right to withdraw from the study at any time without prejudice. Subjects may also be withdrawn from the study by study investigators if they have a recurrent stroke, a symptomatic hemorrhagic transformation of the index ischemic stroke, or another major illness requiring hospitalization, if they become pregnant, or if they are not able to comply with the study protocol or return for routine and study-specific neurological or ophthalmological assessments. Subjects withdrawn from the study will be replaced.

8. STUDY DRUG ADMINISTRATION AND ASSIGNMENT

8.1. Study Drug

Fluoxetine is an antidepressant medication approved by the U.S. Food and Drug Administration (FDA) for use in several conditions, including major depressive disorder and obsessive-compulsive disorder. During the study, each subject will take 20 mg of

fluoxetine or a matching placebo daily for 90 days. Blinded capsules, identical in appearance and containing either an active dose or a placebo, will be prepared by over-encapsulation. Active doses will consist of a single 20-mg fluoxetine capsule placed inside a larger opaque colored capsule and backfilled with inert lactose powder. Placebo doses will consist of the same opaque colored capsule filled only with lactose. Exemption from Investigational New Drug (IND) regulations was granted by the FDA for the use of fluoxetine in this study on August 18, 2015.

8.2. Dosage of Study Drug

Fluoxetine will be administered by mouth at a daily dose of 20 mg for 90 days. There are no plans to increase or decrease the dose of the drug during the course of the study.

8.3. Subject Enrollment and Randomization

Subjects will be randomized in a ratio of 1:1 to fluoxetine vs. placebo by computer randomization. All study personnel will remain blinded to treatment assignments until the conclusion of the entire study, with the exception of the pharmacist and the statistician. These individuals will not disclose any information regarding the treatment assignment of individual subjects to the study investigators.

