8.6. Emergency Drug Disclosure

The University of Rochester Medical Center Investigational Drug Service will maintain a list of treatment assignments for each subject and disclose this information upon request in case of a medical emergency. Should drug disclosure occur, the subject in question will be withdrawn from the study.

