13. DATA ANALYSIS AND MONITORING

13.1. Sample Size Determination

The currently planned enrollment target of 40 subjects (*i.e.* 20 subjects per arm) is intended to achieve a final sample size of 30 and assumes a dropout rate of 25% during the course of the study. In turn, this estimate is based on the number of acute ischemic stroke patients who presented to Strong Memorial Hospital with an isolated visual field deficit in the previous calendar year (56 patients between January 1, 2015 and December 31, 2015). Previous studies indicate that 50% of patients will experience an improvement in their visual field deficit by 3 months. Based on this rate of spontaneous recovery, a final sample size of 15 subjects per group will provide 80% power to detect an improvement rate of 90% in the actively treated group (*i.e.* a 40% difference between the fluoxetine and placebo groups), using a one-sided χ^2 test with $\alpha = 0.05$. Thus, the planned sample size will be sufficient to detect a moderately large effect and is comparable to sample sizes used in equivalent pilot trials evaluating the efficacy of an FDA-approved drug for a novel application.

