13.3. Data and Safety Monitoring

A data and safety monitoring plan appropriate to the nature, size, and complexity of the study will be used to ensure: 1) an adequate process is in place for the oversight and monitoring of the conduct and progress of the study; 2) important information that may affect the safety or welfare of study subjects is noted and addressed as quickly as possible; and 3) the validity and integrity of the data are protected. The monitoring of data quality and subject safety will follow the National Institute of Neurologic Disorders and Stroke Guidelines for Data and Safety Monitoring in Clinical Trials.

The Principal Investigator will monitor the following elements of the study as part of this data and safety monitoring plan:

- Flow of data acquisition
- Timeliness and completeness of reporting
- Recruitment rates
- Protocol violations
- Serious adverse events

The number and nature of adverse events will be reviewed on a monthly basis by the Principal Investigator, and data will be un-blinded if there is serious concern about either of the treatment groups.

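### Section 8.3 leaves the statistician unblinded throughout, with no written task that needs the codes, while parts of the primary analysis are unspecified

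*Combined protocol and SAP*

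**What the plan says.** Section 8.3 states the general rule: "All study personnel will remain blinded to treatment assignments until the conclusion of the entire study". It then makes two exceptions: "with the exception of the pharmacist and the statistician". One restriction applies to both: "These individuals will not disclose any information regarding the treatment assignment of individual subjects to the study investigators". The section gives no reason for exempting the statistician. On list generation it says only this: "Subjects will be randomized in a ratio of 1:1 to fluoxetine vs. placebo by computer randomization".

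Section 8.6 says that the Investigational Drug Service "will maintain a list of treatment assignments for each subject" and discloses assignments in an emergency. Section 8.4 has the same service prepare active drug and placebo.

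Section 13.2 defines the primary endpoint as a gain of 15 degrees or more in the affected field on Humphrey perimetry at 6 months. It continues: "The primary outcome will be compared between the treatment groups using an upper-tailed two-sample" t test, at alpha 0.05. Section 13.1 sizes the trial with a one-sided chi-square test on proportions.

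**The concern.** The restriction in Section 8.3 protects the investigators from learning assignments. It does not limit how the statistician may use that knowledge in analysis decisions. That matters little when the primary analysis is fully fixed in advance, but here it is not. A yes/no endpoint is paired with a test for means, so an analyst could read the endpoint as a responder status or as a continuous change. The plan is silent on how a 24-2 field becomes a 15-degree result, who is analysed once withdrawn subjects are replaced, and how missing data are treated.

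If these points are settled by someone who knows the arms, the final report cannot show that the choices were independent of treatment.

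**Working it through.** **Step 1. Is there a written task that needs the codes?**

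| Task | Who, according to the plan |
|---|---|
| Preparing drug and placebo | Investigational Drug Service (8.4) |
| Holding the list for emergencies | Investigational Drug Service (8.6) |
| Monthly safety review | Principal Investigator (13.3: "The number and nature of adverse events will be reviewed on a monthly basis by the Principal Investigator") |
| Unblinding on serious concern | Not assigned (13.3) |
| Generating the randomization list | Not assigned (8.3) |
| Interim analysis, sample-size re-estimation, adaptive allocation, unblinded board report | None planned |

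No row gives the statistician a duty that requires the assignments. Two rows are unassigned, so an unstated reason remains possible.

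**Step 2. What does the plan leave unspecified?** Section 13.2 fixes the 6-month time point, the t test and alpha. Section 5.2, item 3, specifies SITA standard 24-2 testing but no rule for a 15-degree gain. Section 7 replaces withdrawn subjects, and Section 13.1 expects 25% dropout (0.25 × 40 = 10 of 40). No section defines the analysis set or a missing-data rule.

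**Step 3. Reproduce the plan's figure.** Inputs from 13.1: 15 per arm, 50% against 90%, one-sided alpha 0.05. The mean rate is 0.70.
- Standard error under the null: √(2 × 0.70 × 0.30 / 15) = 0.1673
- Standard error under the alternative: √((0.25 + 0.09) / 15) = 0.1506
- Power = Φ((0.40 − 1.645 × 0.1673) / 0.1506) = Φ(0.83) = 79.6%

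The stated 80% reproduces, so the sample size is not in dispute.

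**Step 4. Choosing between the two named tests on the 0/1 endpoint.** All outcomes at 15 per arm were enumerated with 50% responding in both arms and a one-sided 0.05 level.
- t test: 4.95%
- Uncorrected chi-square test: 5.04%
- Whichever is favourable: 5.04%

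The tests disagree on two tables only (placebo against fluoxetine responders): 9 against 13, and 2 against 6. For 9 against 13:
- chi-square, as z: 0.2667 / √(0.7333 × 0.2667 × 2/15) = 1.651, above 1.645
- t: 0.2667 / √((0.2400 + 0.1156) / 14) = 1.673, below 1.701

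Each table has probability C(15,9) × C(15,13) / 2³⁰ = 5005 × 105 / 2³⁰. Together that is 1,051,050 / 1,073,741,824 = 0.1%. At 50% against 90%, exact power is 79.3% (t) and 83.4% (chi-square).

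**Step 5. Choosing the form of the endpoint at 6 months.** This step rests on assumptions that are not in the documents: normal change scores, the responder threshold at the median (so 50% respond), 15 analysed per arm, and an analyst who always takes the favourable result. Null trials were simulated in three runs of 100,000. Each single test rejected in about 5%. A t test on the continuous change or a chi-square test on responders, whichever was significant, rejected in 7.3% to 7.5%, about 7.4%.

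**The case against.** The strongest reply is that Section 13.2 does settle the endpoint, time point, test and alpha, so little is left to choose. Much of this stands. The two named tests are nearly interchangeable on 0/1 data. The 7.4% figure needs a continuous-change analysis that Section 13.2 does not describe, although its choice of a t test invites one.

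It is also fair that the plan does not say who runs the primary analysis or derives the 15-degree result. Perimetry is performed by ophthalmic technicians or physicians, who are blinded, and they could make that derivation. In addition, the dated analysis document would by itself remove most of the risk. It would not remove later judgements on exclusions and missing data, so masking the analyst keeps some value.

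A reader might infer four stronger points that the documents do not support:
- **That the exemption has no purpose.** The statistician may generate the list or be meant to unblind on a safety concern. The plan does not say.
- **That 3 months competes with 6 months as the primary time point.** Section 13.1 says "Previous studies indicate that 50% of patients will experience an improvement in their visual field deficit by 3 months", which is a planning rate for spontaneous recovery. Section 13.2 names 6 months only.
- **That the choice of test alone could decide the result, as a comparison with Fisher's exact test might suggest.** The plan does not name that test, and power differences do not measure bias.
- **That arm-aware choices were made or are intended.** Nothing in the documents shows this.

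**Conclusion.** The point holds as a design weakness of modest size. A stated rule gives the statistician access to assignments for the whole study. No written task requires it, and the only safeguard concerns disclosure to investigators. The gaps in Section 13.2 are what make that access matter.

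The opening lies in the form of the endpoint, where one-sided error could rise from 5% to about 7.4% under the Step 5 assumptions. It does not lie in the choice between the two named tests, where error stays at 5.04% or below. The effect of an open derivation rule, analysis set and missing-data rule was not quantified, because the documents give no basis for it. The whole point is conditional on the unblinded statistician being the person who settles these items.

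**What to change.** Amend Section 8.3 so that the Investigational Drug Service, or another person who does not perform the primary analysis, generates and holds the key. The analysing statistician stays blinded, or works on masked A/B codes, until database lock. If an unblinded statistician is needed, state the task and separate it from the primary analysis.

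Before the key is released, fix in a dated document: the endpoint form (responder or continuous), the 15-degree derivation from the 24-2 field, one primary test, the analysis set including replaced subjects, and the missing-data rule. Masked labels still show whether the groups differ, so this document should preferably precede any tabulation of outcomes by label.

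The cost is a short amendment and a short analysis document, with no added patients. If the statistician now generates the list, that task passes to the drug service or another existing person.
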